6.3. Appendix 3: Tipping point analysis

A tipping point analysis will be applied by applying an unfavorable additive shift (referred to as delta adjustment) to values imputed to fill in the missing and unobservable data that occur in presence of ICEs. Delta adjustment will be applied only to imputed values in the elinzanetant arm. No delta adjustment will be applied to missing values that occur outside of the time frame of any ICE. The following steps will be implemented for primary endpoint, i.e., frequency of HF:

- 1. The imputation step will be done as described in Section 4.2.1.
- 2. Prior to the analysis step, each imputed value in the elinzanetant arm that occurs in the time frame of an ICE would have a value of "delta" added to it (see Section 4.2.2 for settings of delta for each type of endpoint). The same value of delta will be applied at each time point.
- 3. Observed, imputed, and adjusted data will be analyzed and results combined as described in Section 4.2.1.
- 4. The steps for imputation, modeling, combining the results will be repeated with increasing settings of "delta" (see Section 4.2.1) for each primary endpoint until the estimated treatment difference at Week 4 or Week 12 is no longer statistically significant at the 0.025 one-sided level. The corresponding "delta" setting will be selected as the tipping point for that endpoint.

6.4. Appendix 4: Details regarding the identification of intercurrent events

6.4.1. Temporary treatment interruption

Per definition (see Section 1.1), the ICE "temporary treatment interruption" will only be considered for week 1, week 3 and 4, week 7 and 8, and week 11 and 12. Specifically, temporary treatment interruption is defined as

- Treatment taken on <5/7 days during week 1 for Week 1
- Treatment taken <80% during weeks 1-4 OR treatment taken on <5/7 days during either week 3 or 4 for Week 4

version 3.0 Page: 69 of 87

- Treatment taken <80% during weeks 1-8 OR treatment taken on <5/7 days during either week 7 or 8 for Week 8
- Treatment taken <80% during weeks 1-12 OR treatment taken on <5/7 days during either week 11 or 12 for Week 12.

The criterion for treatment taken on 5/7 days during the corresponding two weeks, as defined above, is met, if in any selected 7 consecutive days within those weeks, the treatment has been taken for less than 5 days (i.e., at least 3 missed intakes).

If the criterion is met, an ICE flag will be placed for the corresponding visit week for HFDD. For PROMIS and MenQoL, the ICE flag will be placed only if the questionnaire is filled in after the third drug missed intake day.

To identify whether < 80 % treatment was taken, planned compliance during weeks 1-4 will be calculated as

100 * Number of capsules taken / 56

where 56 is based on two tablets per day over 28 days. Planned compliance during weeks 1-8 will be calculated as

100 * Number of capsules taken / 112

where 112 is based on two capsules per day over 56 days.

Planned compliance during weeks 1-12 will be calculated as

100 * Number of capsules taken / 168

where 168 is based on two capsules per day over 84 days.

To calculate the number of days per week with treatment intake, a day where at least one capsule was taken, will be considered as a day with treatment intake.

For the identification of the ICE temporary treatment interruption, the compliance and daily treatment intake will be calculated based on the ePRO instrument 'Study drug intake documentation'.

Regarding the reasons, AEs that lead to a treatment interruption, together with start and end date, will be collected on the respective eCRF page. Similarly, reasons related to COVID-19 or administrative reasons will also be collected in the eCRF.

The reasons for temporary treatment interruption will be reviewed during blind review of the data. The observed temporary treatment interruptions together with the corresponding reason will be presented in data listings.

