# 6.4 Study Intervention Compliance

When participants self-administer study intervention(s) at home, compliance with study intervention will be assessed at each visit. Compliance will be assessed by review of daily diary entries and confirmatory capsule counts during study visits and documented in the source documents and relevant form. Deviation(s) from the prescribed dosage regimen should be recorded.

A record of the quantity of study intervention dispensed to and administered by each participant must be maintained and reconciled with study intervention and compliance records. Intervention start and stop dates, including dates for intervention delays will also be recorded. If the participant is unable to continue taking the study intervention as required, she should contact the study site.

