VMS = Vasomotor symptoms

^{*}Please see Section 4.4.1 for the definition of treatment response.

^{**}Exploratory endpoints in addition to listed in the protocol.

version 3.0 Page: 14 of 87

Estimands

The attributes of the main estimand for the primary endpoints are as following:

- Population: women aged 18-70 with VMS caused by adjuvant endocrine therapy, as described by the inclusion/exclusion criteria detailed in the protocol.
- Variable: Efficacy will be assessed based on 2 primary endpoints as listed below:
 - o Change in frequency of moderate to severe HFs from baseline to Week 4
 - o Change in frequency of moderate to severe HFs from baseline to Week 12.
- Treatment: 120 mg elinzanetant, placebo
- ICEs: see Table 1–2 (for further details regarding the identification of ICEs see Section 6.4)

Table 1-2: Primary Estimand: ICEs and Strategies to Address Them

ICEs ^a	Reason for ICE	Strategy	Data handling method
Temporary Treatment interruption ^b	AEs (treatment related/unrelated)	Treatment policy	Utilise the collected data after ICE.
	COVID-19 and administrative reasons	Treatment policy	Utilise the collected data after ICE.
Permanent discontinuation of randomized treatment	AEs (treatment related/unrelated) or Lack of efficacy		
	 For participants who remained untreated/on background therapy. 	Treatment policy	Utilise the collected data after ICE.
	 For participants who initiate alternative VMS treatment 	Treatment policy	Utilise the collected data after ICE.
	Other treatment- unrelated reasons, including COVID-19	Treatment policy	Utilise the collected data after ICE.
Intake of prohibited concomitant medication having impact on efficacy	All reasons	Treatment policy	Utilise the collected data after ICE.
Interruption/ discontinuation in intake of adjuvant endocrine therapy ^c	All reasons	Treatment policy	Utilise the collected data after ICE.

version 3.0 Page: 15 of 87

Table 1-2: Primary Estimand: ICEs and Strategies to Address Them

ICEs ^a	Reason for ICE	Strategy	Data handling method
AE = Adverse ev	ent, COVID-19 = Corona	virus disease	of 2019, ICE = Intercurrent event, VMS =
Vacomotor e	vmntome		

- a) ICEs will be reviewed at the Blinded Review Meeting prior to the study unblinding
- b) Definition of temporary treatment interruption:
- Week 1 = Treatment taken on <5/7 days during week 1 (day 2-8).
- Week 4 = Treatment taken <80% during weeks 1-4 (day 1-28) OR treatment taken on <5/7 days during either Week 3 or 4.

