1	Intake of prohibited medications Any reason	Hypothetical strategy If participant did not take prohibited concomitant medication. Discard the collected data after the intake of prohibited medication(s) for a certain time frame based on the medication class (See Section 6.4.2 for details).	Participants, from the same arm, who comply with treatment regimen ^b and have observed data at the time point that requires imputation.
	Temporary treatment interruption ^a	Hypothetical strategy If participant complied with treatment.	
	Due to COVID-19/ administrative or any other treatment unrelated reasons	Data collected for a specific assessment during/after a temporary treatment interruption will be discarded for that assessment Week only.	

version 3.0 Page: 37 of 87

2	Temporary treatment interruption ^a Due to AE	Treatment policy strategy Utilize all the collected data in the analysis.	Participants, from the same arm, who have available data before and during the treatment interruption. MI will be used to model change from a time point before treatment interruption to a time point with treatment interruption (Copy Increment from Reference imputation
3	Permanent treatment discontinuation	Treatment policy/Hypothetical strategy	Missing values that occur after the ICE will be imputed using a similar MI
	Due to AE/lack of efficacy	If participant remained untreated/on background therapy after permanent discontinuation of the randomized treatment, use the treatment policy strategy and utilize the collected data.	model as used in the main analysis of the primary endpoint, i.e., the wash-out method (Wang et al. 2023).
		Otherwise, if participant initiated an alternative treatment, use the hypothetical strategy under the hypothetical scenario "If participant did not initiate an alternative treatment after permanent discontinuation of randomized treatment". Discard data after the ICE.	
4	Permanent treatment discontinuation Due to COVID-19/ administrative or any other treatment unrelated reasons	Hypothetical strategy If participant did not discontinue the randomized treatment due to the specified reason. Any data collected after permanent treatment discontinuation will be discarded.	All other participants from the same arm (i.e., participants without a similar ICE at the time point that requires imputation).
	Interruption/Discontinuat ion in intake of adjuvant endocrine therapy	Hypothetical strategy If participant did not stop adjuvant endocrine therapy	

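### SAP 6.4.1 flags temporary interruption over any 7 consecutive days, the estimand tables by named week, and its diary-only derivation has no rule for days without an entry

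*SAP*

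**What the plan says.** **The window.** Protocol Table 3-2 and SAP Tables 1-2, 4-4 and 4-6 define the Week 4 event partly by "treatment taken on <5/7 days during either Week 3 or 4". Week 12 is worded the same way with Weeks 11 and 12; the SAP adds Week 8. SAP 6.4.1 refers back to Section 1.1 and repeats this wording. It then gives a different operational rule that spans the pair of weeks. A woman has the event whenever "in any selected 7 consecutive days within those weeks, the treatment has been taken for less than 5 days".

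**The data source.** For this event, SAP 6.4.1 states that "compliance and daily treatment intake will be calculated based on the ePRO instrument 'Study drug intake documentation". The 80% rule for Weeks 1-4 is "100 * Number of capsules taken / 56", and the denominators for Weeks 1-8 and 1-12 are 112 and 168. A day counts as an intake day if at least one capsule was taken. Nothing is said about a day with no entry. Protocol 6.4 assesses compliance by "review of daily diary entries and confirmatory capsule counts during study visits". SAP 4.5.1 uses the eCRF drug accountability and exposure pages as well as the diary. SAP 4.5.1.1 puts available diary data in the denominator for endocrine therapy.

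**The use of the flag.** SAP 4.2.1 applies treatment policy to every intercurrent event in the main analysis. In SAP Tables 4-5 and 4-7, an interruption due to an adverse event keeps its data. For COVID-19, administrative or other treatment-unrelated reasons: "Data collected for a specific assessment during/after a temporary treatment interruption will be discarded for that assessment Week only". Table 4-4 names only COVID-19 and administrative reasons.

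**The concern.** The estimand and its derivation should identify the same women. Here the derivation section claims the estimand's definition and then widens it. SAP Section 1 and Section 4.8 both report no changes from the protocol's analyses, so the widening is not declared.

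The diary-only source adds a second problem. Drug intake is recorded with the evening diary. A woman who took every capsule but left several evening entries blank has capsules missing from the numerator of the 80% rule. Under the 5-of-7 rule she may be scored as having missed days, depending on how the programmer treats a blank.

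At stake are the intercurrent event counts by week and arm (SAP 4.1.3) and both supplementary estimands, which serve the primary and key secondary endpoints. A flag classed as unrelated to treatment removes that week's observed value and takes the woman out of the complier reference group. SAP 6.2 also lets women with such flags and observed data inform the model for outcomes during interruption. A misflagged adherent woman would then represent what happens off drug.

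**Working it through.** **1. The plan's own figures.** Two capsules a day over 28, 56 and 84 days give 56, 112 and 168. These reproduce. Falling below 80% needs at least 6, 12 or 17 fully missed days (0.8 × 28 = 22.4, 0.8 × 56 = 44.8, 0.8 × 84 = 67.2).

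**2. The two windows over 14 days.** The named-week rule tests 2 fixed blocks. The rolling rule tests the 8 possible 7-day windows. Either flags at 3 or more missed days.

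- Exactly 3 missed: C(14,3) = 364 patterns. Named week: 2 × C(7,3) = 70. Rolling: all three days must fall within 7 consecutive days. Counting by the first missed day gives 8 × C(6,2) + C(5,2) + C(4,2) + C(3,2) + C(2,2) = 120 + 10 + 6 + 3 + 1 = 140.
- Exactly 4 missed: C(14,4) = 1001 patterns. Named week: all except the 2 + 2 splits, 1001 − C(7,2)² = 1001 − 441 = 560. Rolling, by full enumeration: 805.
- Five or more missed: one week must contain at least 3, so the rules agree.

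Every named-week flag is also a rolling flag. Week 1 is a single week and is unaffected. Example: missing days 76 and 77 (Week 11) and day 78 (Week 12) is an event under 6.4.1 and not under Table 1-2.

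**3. What the extra flags cost.** A rolling-only flag has at most 2 missed days in each week. If those are the only days without an evening entry, the assessment week still has at least 5 of 7 diary days, and the SAP sets a hot-flash week to missing only when more than 2 days are missing. The hot-flash value is therefore observed, and it is the value that would be discarded.

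**4. Size in an adherent woman.** Assumptions, none given in the documents: each evening entry is absent with probability q, independently, and an absent entry is scored as not taken. The difference between the rules is 70q³(1−q)¹¹ + 245q⁴(1−q)¹⁰, where 70 = 140 − 70 and 245 = 805 − 560. At q = 0.10 this is 0.0220 + 0.0085 = 0.0305.

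| Diary completion | 5-of-7 rule, named week | 5-of-7 rule, rolling | Full Week 12 flag, named week | Full Week 12 flag, rolling |
|---|---|---|---|---|
| 95% | 0.75% | 1.34% | 0.7% | 1.3% |
| 90% | 5.1% | 8.1% | 5.4% | 8.5% |
| 85% | 14.2% | 20.6% | 22.2% | 27.4% |

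The first two result columns are exact. The last two add the 80% rule and come from 200,000 simulated participants. For 405 randomised women, the 5-of-7 rule alone would flag 405 × 0.0507 = 20.5 against 405 × 0.0812 = 32.9 at 90% completion, and 3.0 against 5.4 at 95%. If absent entries are not scored as missed doses, an adherent woman has no flag under either window.

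**The case against.** A reader might infer that the SAP scores every missing diary entry as a missed dose, and that adherent women are therefore flagged and lose their data. The documents do not support that. No section states how a blank day counts under the 5-of-7 rule. Only the 80% rule, by its arithmetic, gives unrecorded capsules a value of zero. The primary estimand and the main key secondary analyses use all collected data, and the washout imputation in SAP 4.2.1 concerns data missing after permanent discontinuation. No confirmatory test depends on this flag.

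Even in the supplementary analyses, discarding needs a treatment-unrelated reason. An adherent woman would normally have no reason recorded, and no section assigns such a flag to a category.

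There are also safeguards: device alarms, late entry until 10:59 AM the next day, site contact after consecutive missed entries, and blind review of intercurrent events and of interruption reasons. PROMIS and MENQOL are flagged only if completed after the third missed intake. Table 1-2 refers to Section 6.4 for identifying events, so a programmer would probably follow 6.4.1.

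Most of this stands, and it limits the size. It does not remove the conflict: following 6.4.1 means departing from the estimand's stated definition. The review of reasons is not described as checking flags against capsule counts. Independence of missed entries is also an assumption; lost devices or illness would cluster blanks and often remove the morning entry too, leaving less observed data to discard.

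**Conclusion.** The window conflict is established from the text and needs no assumption: the rolling rule doubles the flagged patterns with 3 missed days and raises those with 4 from 560 to 805 of 1001. The incomplete derivation rule is also established: diary only, fixed denominators, no instruction for blank days, and no use of the accountability data that SAP 4.5.1 uses.

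That an adherent woman can be flagged follows from these gaps; how often depends on diary completion and on how blanks are scored. With blanks scored as missed, it is about 1% at 95% completion and 8% at 90% for Week 12. The part due to the window alone is about 0.6 percentage points at 95% and 3 at 90%.

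The consequence is limited to the event counts and the two supplementary estimands, for the affected week and for flags not due to an adverse event. It merits correction because these analyses are meant to test the main result under other assumptions, and the correction is cheap.

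**What to change.** 1. Use the named-week rule of the estimand tables in SAP 6.4.1. Alternatively, amend all the tables to the rolling rule and list it in SAP 4.8 as a change from the protocol. Either resolves the conflict; the first needs no change to the protocol's definition.
2. State how a day without an entry is scored. Do not score it as missed when the eCRF accountability count for that dispensing interval shows full use. Interval counts cannot date a missed dose, so where capsules remain and the missed days cannot be placed, decide the flag at the blind review.
3. State which category a flag with no recorded reason belongs to, and align Table 4-4 with Tables 4-5 and 4-7.

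The cost is SAP wording and some derivation work; the data are already collected. The downside is that a few true missed doses on days without an entry may go unflagged.

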6.4.2. Permanent discontinuation of randomized treatment

The reasons for permanent discontinuation of randomized treatment will be collected on the corresponding eCRF page, among others with AE or lack of efficacy as possible options. A permanent discontinuation of randomized treatment will be considered to be due to "other treatment unrelated reasons" if AE or lack of efficacy was not selected as reason and any of the following was selected:

Non-compliance with study device

version 3.0 Page: 70 of 87

- Site terminated by sponsor
- Technical problems
- Pregnancy
- Subject decision
- Subject decision: unwillingness to comply with study procedures
- Lost to follow-up
- Other
- COVID-19 pandemic related: subject specific
- COVID-19 pandemic related: other
- Non-compliance with study drug
- Randomized by mistake

The observed permanent discontinuations of randomized treatment together with corresponding reason will be presented in data listings.

Discontinuation due to AE or lack of efficacy may be handled differently depending on estimand for participants who remained untreated/background therapy and for participants who initiate alternative VMS treatment. The treatment status (i.e., remained untreated/on background therapy vs. initiate alternative VMS treatment) should be captured for all participants who discontinued from randomized drug irrespective of the reason for discontinuation.

Table 6–3: Preliminary list of alternative VMS treatment (can be updated during blind review meeting)

				I		1
DGCODEL0	DGNAME0	DGCODEL1	DGNAME1	DGCODEL2	DGNAME2	Duration of
						impact with
						respect to
						efficacy ^a
						(considered up
						to 12 weeks ^b)
		5	Hormone	2	Oestrogens	1, From 1st
			replacement			dose to 4 weeks
			therapy			after the last
						dose if the route
						is vaginal,
						intravaginal,
						cutaneous,
						nasal or
						transdermal.
						2, From 1st
						dose to 8 weeks
						after the last
						dose if the route

Page: 71 of 87 version 3.0

						is oral, sublingual or intrauterine, 3, From 1st dose to 12 weeks or longer if the route is subcutaneous or intradermal.
		5	Hormone replacement therapy	3	Progestogens	1, From 1st dose to 4 weeks after the last dose if the route is vaginal, intravaginal, cutaneous, nasal or transdermal. 2, From 1st dose to 8 weeks after the last dose if the route is oral, sublingual or intrauterine, 3, From 1st dose to 12 weeks or longer if the route is subcutaneous, intradermal or intramuscular.
1633	Drugs for psychiatric disorders	111	Antidepressants	113	Selective serotonin reuptake inhibitors (SSRI)	From 1st dose to 4 weeks after the last dose

^{*}In this column, the terms "1st dose" and "last dose" both refer to the start date and stop date of certain doses of concomitant medication. If the dose was changed, a new start date and/or stop date were reported.

** No further differentiation if duration of impact is longer than 12 weeks since ICEs are considered in the analysis only for the first 12 weeks of the study.

version 3.0 Page: 72 of 87

Table 6–4: Preliminary list of alternative VMS treatment by drug names (can be updated during blind review meeting)

WHO Drug Name	WHO Drug Record Number	WHO Drug Sequence Number 1	WHO Drug Sequence Number 2	Duration of impact with respect to efficacy ^a (considered up to 12 weeks ^b)
OXYBUTIN	005389	02	057	From 1st dose to 4 weeks after the last dose

^aIn this column, the terms "1st dose" and "last dose" both refer to the start date and stop date of certain doses of concomitant medication. If the dose was changed, a new start date and/or stop date were reported.

Although more alternative treatment options may be available, only drug groupings/ drug names are listed that were reported in OASIS 1-4 studies as of finalization of this statistical analysis plan.

6.4.3. Intake of prohibited concomitant medication having impact on efficacy

Drug groupings, individual drugs and manual review will be used to identify whether any prohibited concomitant medication as defined in the protocol were used that influence efficacy. All here listed drug groupings/ drug names were reported in OASIS 1-4 studies as of finalization of this statistical analysis plan, although other medications may also be prohibited per the protocol.

- 1. For the change from baseline at Week 1 any intake of prohibited medication during Week 1 that has an effect on HF will be considered an intercurrent event.
- 2. For weeks 4, 8, and 12, not only intake in the respective week but also, intake that occurred prior to week 4, 8, and 12 should be considered as an intercurrent event if within the washout period of the prohibited drug.

A similar approach will be used for the endpoints related to sleep quality (mean change in PROMIS SD SF 8b total score from baseline) and to the menopause related quality of life (mean change in MENQOL total score from baseline) with respect to any prohibited medication that has an effect on sleep quality and menopause related quality of life, respectively.

The list of prohibited concomitant medication together with the assumed relevant time period for their effect will be reviewed during blind review of the data and finalized prior to unblinding.

^b No further differentiation if duration of impact is longer than 12 weeks since ICEs are considered in the analysis only for the first 12 weeks of the study.

version 3.0 Page: 73 of 87

Table 6–5: Preliminary list of prohibited concomitant medication by drug grouping (can be updated during the blind review meeting)

Any additional condition, so that considere d as prohibite d and considere d as intercurre nt event	DGCODEL0	DGNA ME0	DGCODE L1	DGNAME1	DGCODEL2	DGNAME2	Duration of impact with respect to efficacy ^a (considered up to 12 weeks ^b)
If newly started or dose modified or stopped during the first 12 weeks of study period			5	Hormone replacement therapy	2	Oestrogens	1, From 1st dose to 4 weeks after the last dose if the route is vaginal, intravaginal, cutaneous, nasal or transdermal. 2, From 1st dose to 8 weeks after the last dose if the route is oral, sublingual or intrauterine, 3, From 1st dose to 12 weeks or longer if the route is subcutaneous or intradermal.
If newly started or dose modified or stopped during the first 12 weeks of study period			5	Hormone replacement therapy	3	Progestogens	1, From 1st dose to 4 weeks after the last dose if the route is vaginal, intravaginal, cutaneous, nasal or transdermal. 2, From 1st dose to 8 weeks after the last dose if the route is oral, sublingual or intrauterine, 3, From 1st dose to 12 weeks or longer if the route is subcutaneous,

Statistical Analysis Plan BAY 3427080 / 21656 version 3.0

version 3.0 Page: 74 of 87

							intradermal or intramuscular.
Any other than tamoxifen or aromatase inhibitor or GnRH agonists and GnRH antagonist; if newly started or dose modified or stopped during the first 12 weeks of study period			772	Cancer therapies	738	Endocrine antineoplastic therapy	From 1st dose to 12 weeks after the last dose (All other cancer therapies are excluded, only tamoxifen, aromatase inhibitors, GnRH agonists and GnRH antagonist are allowed.°)
If newly started or dose modified or stopped during the first 12 weeks of study period	1633	Drugs for psychi atric disord ers	111	Antidepressants	114	Monoamine oxidase (MAO) inhibitors, non- selective	From 1st dose to 4 weeks after the last dose
If newly started or dose modified or stopped during the first 12 weeks of study period	1633	Drugs for psychi atric disord ers	111	Antidepressants	115	Monoamine oxidase A (MAO-A) inhibitors	From 1st dose to 4 weeks after the last dose

Statistical Analysis Plan BAY 3427080 / 21656 version 3.0

rersion 3.0 Page: 75 of 87

If newly started or dose modified or stopped during the first 12 weeks of study period	1633	Drugs for psychi atric disord ers	111	Antidepressants	112	Non-selective monoamine reuptake inhibitors	From 1st dose to 4 weeks after the last dose
If newly started or dose modified or stopped during the first 12 weeks of study period	1633	Drugs for psychi atric disord ers	111	Antidepressants	113	Selective serotonin reuptake inhibitors (SSRI)	From 1st dose to 4 weeks after the last dose
	45	Drugs interac ting with CYP3 A	240	CYP3A inducers	225	Moderate CYP3A inducers	From 1st dose to 4 weeks after the last dose Considered not to have an influence on efficacy, if route is auricular(otic), ophthalmic or conjunctival.
	45	Drugs interac ting with CYP3	240	CYP3A inducers	265	Strong CYP3A inducers	From 1st dose to 4 weeks after the last dose
If newly started or dose modified or stopped during the first 12 weeks of	1633	Drugs for psychi atric disord ers	111	Antidepressants	1830	Antidepressant Serotonin Norepinephrine Reuptake Inhibitors (SNRI)	From 1st dose to 4 weeks after the last dose

version 3.0 Page: 76 of 87

study				
period				

^aIn this column, the terms "1st dose" and "last dose" both refer to the start date and stop date of certain doses of concomitant medication. If the dose was changed, a new start date and/or stop date were reported.

In addition, the following concomitant medications are considered prohibited:

Table 6–6: Preliminary list of prohibited concomitant medication by drug names (can be updated during the blind review meeting)

Any additional condition, so that considered as prohibited and considered as intercurrent event	WHO Drug Name	WHO Drug Record Number	WHO Drug Sequence Number 1	WHO Drug Sequence Number 2	Duration of impact with respect to efficacy ^a (considered up to 12 weeks ^b)
If newly started or dose modified or stopped during the first 12 weeks of study period	ARMOUR THYROID	000537	01	011	From 1st dose to 12 weeks after the last dose
If newly started or dose modified or stopped during the first 12 weeks of study period	NATURE THROID	000537	01	027	From 1st dose to 12 weeks after the last dose
If newly started or dose modified or stopped during the first 12 weeks of study period	LEVOTHYROXINE	000680	01	001	From 1st dose to 12 weeks after the last dose
If newly started or dose modified or stopped during the first 12 weeks of study period	L-THYROXINE	000680	01	006	From 1st dose to 12 weeks after the last dose
If newly started or dose modified or stopped during the first 12 weeks of study period	L-THYROXIN	000680	01	014	From 1st dose to 12 weeks after the last dose
If newly started or dose modified or stopped	LEVAXIN	000680	02	002	From 1st dose to 12 weeks after the last dose

^b No further differentiation if duration of impact is longer than 12 weeks since ICEs are considered in the analysis only for the first 12 weeks of the study.

^c Tamoxifen (ATC =L02BA), aromatase inhibitors (ATC = L02BG), GnRH agonists (DGCODEL1 = 108, DGCODEL2 = 109) GnRH antagonists (DGCODEL1 = 108, DGCODEL2 = 110)

Page: 77 of 87

	T	T	ı	ı	
during the first 12 weeks of study period					
If newly started or dose modified or stopped during the first 12 weeks of study period	SYNTHROID	000680	02	005	From 1st dose to 12 weeks after the last dose
If newly started or dose modified or stopped during the first 12 weeks of study period	EUTHYROX	000680	02	007	From 1st dose to 12 weeks after the last dose
If newly started or dose modified or stopped during the first 12 weeks of study period	THYROXIN	000680	02	014	From 1st dose to 12 weeks after the last dose
If newly started or dose modified or stopped during the first 12 weeks of study period	LEVOTHYROXINE [LEVOTHYROXINE SODIUM]	000680	02	020	From 1st dose to 12 weeks after the last dose
If newly started or dose modified or stopped during the first 12 weeks of study period	THYREX	000680	02	028	From 1st dose to 12 weeks after the last dose
If newly started or dose modified or stopped during the first 12 weeks of study period	THYROHORMONE	000680	02	029	From 1st dose to 12 weeks after the last dose
If newly started or dose modified or stopped during the first 12 weeks of study period	Т4	000680	02	031	From 1st dose to 12 weeks after the last dose
If newly started or dose modified or stopped during the first 12 weeks of study period	LETROX	000680	02	046	From 1st dose to 12 weeks after the last dose
If newly started or dose modified or stopped during the first 12 weeks of study period	UNITHROID	000680	02	052	From 1st dose to 12 weeks after the last dose

ersion 3.0 Page: 78 of 87

	T		,		
If newly started or dose modified or stopped during the first 12 weeks of study period	LEVOTIROXINA [LEVOTHYROXINE SODIUM]	000680	02	054	From 1st dose to 12 weeks after the last dose
If newly started or dose modified or stopped during the first 12 weeks of study period	L-THYROXIN HENNING	000680	02	058	From 1st dose to 12 weeks after the last dose
If newly started or dose modified or stopped during the first 12 weeks of study period	TIROXIN [LEVOTHYROXINE SODIUM]	000680	02	062	From 1st dose to 12 weeks after the last dose
If newly started or dose modified or stopped during the first 12 weeks of study period	L THYROXIN	000680	02	070	From 1st dose to 12 weeks after the last dose
If newly started or dose modified or stopped during the first 12 weeks of study period	EUTIROX	000680	02	074	From 1st dose to 12 weeks after the last dose
If newly started or dose modified or stopped during the first 12 weeks of study period	LEVOTHYROXIN	000680	02	081	From 1st dose to 12 weeks after the last dose
If newly started or dose modified or stopped during the first 12 weeks of study period	TIROSINT	000680	02	087	From 1st dose to 12 weeks after the last dose
If newly started or dose modified or stopped during the first 12 weeks of study period	EUTHYROX N	000680	02	138	From 1st dose to 12 weeks after the last dose
If newly started or dose modified or stopped during the first 12 weeks of study period	LEVOTIROXIN	000680	02	145	From 1st dose to 12 weeks after the last dose
If newly started or dose modified or stopped	L THYROX	000680	02	163	From 1st dose to 12 weeks after the last dose

Page: 79 of 87

during the first 12 weeks of study period					
If newly started or dose modified or stopped during the first 12 weeks of study period	TIROSINT SOL	000680	02	219	From 1st dose to 12 weeks after the last dose
If newly started or dose modified or stopped during the first 12 weeks of study period	LIOTHYRONINE	001433	01	001	From 1st dose to 12 weeks after the last dose
If newly started or dose modified or stopped during the first 12 weeks of study period	LIOTHYRONIN	001433	02	020	From 1st dose to 12 weeks after the last dose
	CLONIDINE	001711	01	001	From 1st dose to 4 weeks after the last dose
	CLONIDINE HYDROCHLORIDE	001711	02	001	From 1st dose to 4 weeks after the last dose
	DIXARIT	001711	02	002	From 1st dose to 4 weeks after the last dose
	CLONIDINE HCL	001711	02	048	From 1st dose to 4 weeks after the last dose
	CANNABIS SATIVA	002377	01	001	From 1st dose to 4 weeks after the last dose
	CANNABIS SATIVA	002377	01	002	From 1st dose to 4 weeks after the last dose
	MARIJUANA	002377	01	002	From 1st dose to 4 weeks after the last dose
	CBD OEL	002377	08	003	From 1st dose to 4 weeks after the last dose
	OXYBUTIN	005389	02	057	From 1st dose to 4 weeks after the last dose
	DRIPTAN	005389	02	126	From 1st dose to 4 weeks after the last dose

Page: 80 of 87

	T	T			
	GABAPENTIN	010030	01	001	From 1st dose to 4 weeks after the last dose
	NEURONTIN [GABAPENTIN]	010030	01	002	From 1st dose to 4 weeks after the last dose
	GABRION	010030	01	024	From 1st dose to 4 weeks after the last dose
	GABAPENTINE	010030	01	045	From 1st dose to 4 weeks after the last dose
	GABA [GABAPENTIN]	010030	01	226	From 1st dose to 4 weeks after the last dose
	PREGABALIN	016141	01	001	From 1st dose to 4 weeks after the last dose
	LYRICA	016141	01	002	From 1st dose to 4 weeks after the last dose
	PRAGIOLA	016141	01	249	From 1st dose to 4 weeks after the last dose
	EGZYSTA	016141	01	314	From 1st dose to 4 weeks after the last dose
	PREATO	016141	01	722	From 1st dose to 4 weeks after the last dose
	CANNABIDIOL	079492	01	001	From 1st dose to 4 weeks after the last dose
If newly started or dose modified during the first 12 weeks of study period	THYRONAJOD	109689	02	006	From 1st dose to 12 weeks after the last dose
If newly started or dose modified during the first 12 weeks of study period	LEVOTHYROXINE;P OTASSIUM IODIDE	109689	03	001	From 1st dose to 12 weeks after the last dose
If newly started or dose modified during the first 12 weeks of study period	LEVOTHYROXINE AND LIOTHYRONINE [LEVOTHYROXINE;LI OTHYRONINE]	131345	01	008	From 1st dose to 12 weeks after the last dose

Statistical Analysis Plan BAY 3427080 / 21656

version 3.0 Page: 81 of 87

If newly started or dose modified during the first 12 weeks of study period	NOVOTHYRAL	131345	03	007	From 1st dose to 12 weeks after the last dose
---	------------	--------	----	-----	---

^a In this column, the terms "1st dose" and "last dose" both refer to the start date and stop date of certain doses of concomitant medication. If the dose was changed, a new start date and/or stop date were reported.

